6.1 Treatment

6.1.1 Identity of Investigational Product

Tofacitinib is an orally administered, synthetic small molecule that selectively inhibits the JAK family of kinases, and is currently FDA approved for the treatment of rheumatoid arthritis (RA), psoriatic arthritis (PsA), and ulcerative colitis (UC). Unlike targeted biologic therapies, which are directed at extracellular targets such as individual soluble cytokines (e.g. TNF- α), cytokine receptors (IL-1R, IL-6R) or other cell surface receptors (CD20, CD80, and CD86), tofacitinib works intracellularly⁹ and has been developed to target a number of cytokines known to have a role in inflammatory diseases.

SOC will be determined by YNHH SARS-CoV-2 Therapeutics Group and may include treatment targeting SARS-CoV-2 (e.g., anti-viral therapies). However, those enrolled in our study will not receive other forms of IL-6 blocking agents (e.g. tocilizumab, sarilumab, or other JAKi), if these are part of the SOC algorithm (Please see **Appendix 1** for current algorithm).

Study intervention is defined as any investigational intervention(s), marketed product(s), placebo, medical device(s), or study procedure(s) intended to be administered to a study participant according to the study protocol.

For the purposes of this protocol, study intervention refers to Tofacitinib 5 mg tablets.

All participants will receive pharmacologic thromboprophylaxis with LMWH and supportive care for COVID-19 pneumonia. It is acceptable for participants to also receive experimental therapies for COVID-19, with the exception of prohibited medications listed in the eligibility criteria and concomitant medications sections of the protocol.

6.1.2 Dosage, Administration, Schedule

TREATMENT DESCRIPTION

Tofacitinib or placebo will be administered. Tofacitinib will be administered in a dose of 10 mg PO BID until return to their clinical baseline (as defined by supplementary oxygen requirement), and then will continue to be administered at 5 mg PO BID for a total treatment duration of 14 days. Follow-up off tofacitinib will continue up to Day 90.

- Tofacitinib tablets will be sourced from Pfizer, Inc. Matching placebo tablets will be provided by Pfizer, Inc..
- Participants will swallow the study intervention whole and will not manipulate or chew the study intervention prior to swallowing. If the participant is unable to swallow the study intervention whole, tofacitinib 5 mg film-coated tablets will be disintegrated in water (in a syringe) and administered as a liquid suspension through a nasal-gastric (NG) tube or percutaneous endoscopic gastrostomy (PEG) tube. Dosing of the suspension should occur within 4 hours from the time of preparation, when stored at room temperature (15-25°C), or within 24 hours, when at refrigerated temperature (2-8°C). Dosing verification was completed by Pfizer which was demonstrated through in-use stability of the prepared

suspension, compatibility of the suspension with common materials of composition for NG and PEG tubes, and accuracy of the intended dose. Since tofacitinib meets the Biopharmaceutics Class System (BCS) criteria for high solubility designation and the 5 mg IR tablet has been demonstrated to be bioequivalent to 5 mL of the oral solution (1 mg/mL) (Study A3921354 conducted under IND 117,400), we expect that disintegration of the 5 mg tablet in the syringe will not adversely impact the bioperformance.

• Study intervention administration details will be recorded on the CRF.

Intervention Name	Tofacitinib
ARM Name	Tofacitinib plus SoC therapy
Туре	Drug
Dose Formulation	Tablet
Unit Dose Strengths	5 mg
Dosage Level	10 mg BID
Route of Administration	Oral or per nasogastric tube
Use	Experimental
IMP or NIMP	IMP
Sourcing	Provided by Pfizer
Packaging and Labeling	Study intervention will be provided in bottles with appropriate
	labeling.
Current/Former Names or Aliases	CP-690550, Xeljanz [®]

REQUIRED TREATMENT MODIFICATIONS

The following dose adjustments need to be considered during the use of 10 mg BID in this patient population when the potential exists for differences in tofacitinib exposure due to DDI or changes in renal or hepatic function:

- When a concomitantly used drug is a strong CYP3A4 inhibitor, OR when a co-administered drug is both a moderate CYP3A4 inhibitor and a strong CYP2C19 inhibitor (eg, fluconazole), a 50% reduction in dose is recommended. Therefore, a 5 mg BID dose should be used to achieve a similar exposure as that of 10 mg BID in a patient not receiving co-administered metabolic inhibitor.
 - Antivirals such as lopinavir and ritonavir are examples of potent CYP3A4 inhibitors. Cobicistat, which is used to increase concentrations of antiviral drugs, is also a potent CYP3A4 inhibitor. Examples of other co-administered drugs requiring dose reduction are ketoconazole, itraconazole, clarithromycin, telithromycin, and fluconazole (**Appendix 2**).
 - Tofacitinib dose reduction is not needed when co-administered with the following medication: azithromycin, hydroxychloroquine, chloroquine, remdesivir, favipiravir, oseltamivir, and ribavirin.
- A 50% dose reduction is recommended in patients who are in moderate or severe renal impairment (including patients on hemodialysis) and those in moderate hepatic impairment. Therefore 5 mg BID should be used in these patients, which will be

changed to 5 mg PO QD upon return to their clinical baseline (as defined by supplementary oxygen requirement).

- Tofacitinib should not be used in patients with severe hepatic impairment (Participants with Child-Pugh class C are excluded).
- Tofacitinib use is not recommended in patients receiving a potent CYP3A4 inducer (eg, rifampin, St. John's wort) or if they had discontinued use of a potent CYP3A4 inducer less than 28 days or 5 half-lives prior to the first dose of tofacitinib.

Required Tofacitinib Discontinuations:

In rare instances, it may be necessary for a participant to permanently discontinue study intervention (definitive discontinuation). Reasons for definitive discontinuation of study intervention include the following.

- WBC count <1000 /mm3
- Lymphocyte counts <250 cells/mm3.
- Absolute neutrophil counts <500 cells/mm3.
- Hemoglobin less than 8 g/dL.
- ALT or AST ≥5 times the ULN.
- Anaphylaxis or other serious allergic reaction.
- Diagnosis of venous thromboembolism.
- Any serious infection, including secondary bacterial pneumonia, or other safety event for which the investigator determines that continued treatment with tofacitinib is not in the participant's best interest.
- If IL-6 targeting agent or other non-FDA approved, compassionate use or expanded access is considered as medically necessary (AS REVIEWED BY THE PI)
- Diagnosis of thrombosis including pulmonary embolism, deep venous thrombosis, and arterial thrombosis

6.1.3 Preparation/Handling/Storage/Accountability

- 1. The investigator or designee must confirm appropriate temperature conditions have been maintained during transit for all study interventions received and any discrepancies are reported and resolved before use of the study intervention.
- 2. Only participants enrolled in the study may receive study intervention and only authorized site staff may supply or administer study intervention. All study interventions must be stored in a secure, environmentally controlled, and monitored (manual or automated recording) area in accordance with the labeled storage conditions with access limited to the investigator and authorized site staff. At a minimum, daily minimum and maximum temperatures for all site storage locations must be documented and available upon request. Data for nonworking days must indicate the minimum and maximum temperatures since previously documented for all site storage locations upon return to business.

- 3. Any excursions from the study intervention label storage conditions should be reported to Pfizer upon discovery along with any actions taken. The site should actively pursue options for returning the study intervention to the storage conditions described in the labeling, as soon as possible. Once an excursion is identified, the study intervention must be quarantined and not used until Pfizer provides permission to use the study intervention. Specific details regarding the definition of an excursion and information the site should report for each excursion will be provided to the site in the IP manual or other specified location.
- 4. Any storage conditions stated in the SRSD will be superseded by the storage conditions stated on the label.
- 5. Study interventions should be stored in their original containers.
- 6. The investigator, institution, or the head of the medical institution (where applicable) is responsible for study intervention accountability, reconciliation, and record maintenance (ie, receipt, reconciliation, and final disposition records), such as the IPAL or sponsor-approved equivalent. All study interventions will be accounted for using a study intervention accountability form/record.
- 7. Further guidance and information for the final disposition of unused study interventions are provided in the IP manual or other specified location. All destruction must be adequately documented. If destruction is authorized to take place at the investigator site, the investigator must ensure that the materials are destroyed in compliance with applicable environmental regulations, institutional policy, and any special instructions provided by Pfizer.

Upon identification of a product complaint, notify the sponsor within 1 business day of discovery as described in the IP Manual.

6.1.4 Preparation and Dispensing

A qualified staff member (investigational drug service pharmacist) will dispense the study intervention, in quantities appropriate according to the schedule (6.4.1). A second staff member will verify the dispensing.

6.1.5 Method of Assignment/Randomization

The Investigational Drug Service at Yale Center for Clinical Investigation will conduct the randomization. Study will be double blinded.

6.1.6 Blinding and Procedures for Unblinding

This study is blinded. Study intervention and matching placebo tablets will be dispensed in appropriately marked, covered dosing cups to limit the treating physician's knowledge of the treatment.

The research pharmacist will dispense the investigational product and record only the randomization code in the CRF and record the number of tablets each patient will receive independent of group assignment. As such, the research pharmacist will be unblinded.

However, as only the randomization code will be recorded in the CRF, physicians and caregivers will continue to be blinded. Only trained investigators and site staff as recorded on the delegation of authority log will have access to the CRF.

6.1.7 Allocation to Study Intervention

This is a blinded study; potential bias will be reduced by the following steps: randomization provided to site. The investigator's knowledge of the treatment should not influence the decision to enroll a particular participant or affect the order in which participants are enrolled. The site will record the study intervention assignment on the applicable CRF, if required.

Study intervention will be dispensed at the study visits summarized (6.4.1).

Returned study intervention must not be re-dispensed to the participants.

The study-specific IRT reference manual and IP manual will provide the contact information.

6.1.8 Study Intervention Compliance

When the individual dose for a participant is prepared from a bulk supply, the preparation of the dose will be confirmed by a second qualified member of the study site staff.

When participants are dosed at the site, they will receive study intervention directly from the investigator or designee, under medical supervision. The date and time of each dose administered in the clinic will be recorded in the source documents and recorded in the CRF. The dose of study intervention and study participant identification will be confirmed at the time of dosing by a member of the study site staff other than the person administering the study intervention.

When compliance of less than 70% or more than 120% of the expected number of doses of study intervention is suspected, the reason for non-compliance with the dosing regimen should be documented in the dosing log of the participant's case report form, and should be reported as a protocol deviation and unless there is a protocol stipulated reason for non-compliance with the dosing regimen, this should be recorded as a dosing error.

6.1.9 Packaging/Labeling

Clinical supply tablets and placebo will be used.

6.1.10 Storage Conditions

Tablets will be stored at and dispensed by the YNHH inpatient pharmacy or Investigational Drug Service. The pharmacy may convert the active ingredient into a suspension form.

6.1.11 Concomitant therapy

All participants must receive pharmacologic thromboprophylaxis with LMWH and supportive care for COVID-19 pneumonia. It is acceptable for participants to also receive experimental therapies with the exception of prohibited medications listed in the eligibility criteria and concomitant medications sections of the protocol. To the extent possible, the following restrictions should be followed:

- Use of strong inhibitors of cytochrome P450 3A should be avoided to the extent possible. Judicious use of strong inhibitors of CYP3A4 or a moderate inhibitor of CYP3A4 that is also a strong inhibitor of CYP2C19 is permitted, if necessary, but the dose of tofacitinib should be reduced to 5 mg BID PO with careful monitoring for adverse effects (see Tofacitinib Dose Modifications).
- Concomitant use of tofacitinib with strong inducers of cytochrome P450 is not recommended, and tofacitinib should not be used if strong inducers have been

discontinued less than 28 days or 5 half-lives prior to the first tofacitinib dose (**Appendix 2**).

- Herbal supplementation should not be administered, as many interfere with the cytochrome P450 pathways.
- Other JAK inhibitors, biological DMARDS, or potent immunosuppressive agents, including IL-6 inhibitors (eg, tocilzumab) and IL-1 inhibitors (eg, anakinra) should not be administered during the study.
- All non-pharmacologic and nutritional supportive care measures, including nutritional supplementation and oxygenation support are permitted. All concomitant medications and nondrug treatments, with dose and frequency, should be recorded.
- Hormonal contraceptives that meet the requirements of this study are allowed to be used in participants who are WOCBP.

Tofacitinib Dose Modifications:

The following dose adjustments need to be considered during the use of 10 mg BID in this patient population when the potential exists for differences in tofacitinib exposure due to DDI or changes in renal or hepatic function:

- When a concomitantly used drug is a strong CYP3A4 inhibitor, OR when a co-administered drug is both a moderate CYP3A4 inhibitor and a strong CYP2C19 inhibitor (eg, fluconazole), a 50% reduction in dose is recommended. Therefore, a 5 mg BID dose should be used to achieve a similar exposure as that of 10 mg BID in a patient not receiving co-administered metabolic inhibitor.
 - Antivirals such as lopinavir and ritonavir are examples of potent CYP3A4 inhibitors. Cobicistat, which is used to increase concentrations of antiviral drugs, is also a potent CYP3A4 inhibitor. Examples of other co-administered drugs requiring dose reduction are ketoconazole, itraconazole, clarithromycin, telithromycin, and fluconazole (**Appendix 2**).
 - Tofacitinib dose reduction is not needed when co-administered with the following medication: azithromycin, hydroxychloroquine, chloroquine, remdesivir, favipiravir, oseltamivir, and ribavirin.
- A 50% dose reduction is recommended in patients who are in moderate or severe renal impairment (including patients on hemodialysis) and those in moderate hepatic impairment. Therefore 5 mg BID should be used in these patients which will be changed to 5 mg PO QD upon return to their clinical baseline (as defined by supplementary oxygen requirement).
- Tofacitinib should not be used in patients with severe hepatic impairment (Participants with Child-Pugh class C are excluded).
- Tofacitinib use is not recommended in patients receiving a potent CYP3A4 inducer (eg, rifampin, St. John's wort) or if they had discontinued use of a potent CYP3A4 inducer less than 28 days or 5 half-lives prior to the first dose of tofacitinib.

6.1.12 Restrictions

None

6.2 Assessments

6.2.1 Efficacy

The primary and secondary endpoints will be assessed during the course of the study for each subject enrolled. These are outlined separately. Data will be gathered through daily review of the medical records, including vital signs, ventilatory requirements, laboratory values, and additional clinical findings.

6.2.2 Safety and Pregnancy-related policy

Urine pregnancy testing for women of childbearing potential will be performed. Women who are pregnant or breast feeding will be excluded.

6.2.3 Adverse Events Definition and Reporting

Definitions

Adverse event (AE) means any untoward medical occurrence associated with the use of an intervention in humans, whether or not considered intervention-related (21 CFR 312.32 (a)).

Any new infection that occurs on study, regardless of the infecting agent (i.e. viral or nonviral) will be captured as an adverse event. Data captured will include site of infection and source of culture (BAL, tracheal aspirate, sputum, blood, urine etc.)

An AE or suspected adverse reaction is considered "serious" (SAE) if, in the view of either the investigator or sponsor, it results in any of the following outcomes:

- death,
- a life-threatening adverse event,
- inpatient hospitalization or prolongation of existing hospitalization,
- a persistent or significant incapacity or substantial disruption of the ability to conduct normal life functions,
- a congenital anomaly/birth defect, or
- An important medical event that may not result in death, be life-threatening, or require hospitalization may be considered serious when, based upon appropriate medical judgment, they may jeopardize the participant and may require medical or surgical intervention to prevent one of the outcomes listed in this definition. Examples of such medical events include allergic bronchospasm requiring intensive treatment in an emergency room or at home, blood dyscrasias or convulsions that do not result in inpatient hospitalization, or the development of drug dependency or drug abuse.

Severity

Adverse events will be graded according to [name grading scale, e.g. CTCAE v5.0]. For AEs not included in the protocol defined grading system, the following guidelines will be used to describe severity.

- Mild Events require minimal or no treatment and do not interfere with the participant's daily activities.
- Moderate Events result in a low level of inconvenience or concern with the therapeutic measures. Moderate events may cause some interference with functioning.

• Severe – Events interrupt a participant's usual daily activity and may require systemic drug therapy or other treatment. Severe events are usually potentially life-threatening or incapacitating. Of note, the term "severe" does not necessarily equate to "serious".]

Relationship to Investigational Product

All AEs must have their relationship to study intervention assessed by the clinician who examines and evaluates the participant based on temporal relationship and his/her clinical judgment. The degree of certainty about causality will be graded using the categories below. In a clinical trial, the study product must always be suspect.

- Definitely Related There is clear evidence to suggest a causal relationship, and other possible contributing factors can be ruled out. The clinical event, including an abnormal laboratory test result, occurs in a plausible time relationship to study intervention administration and cannot be explained by concurrent disease or other drugs or chemicals. The response to withdrawal of the study intervention (dechallenge) should be clinically plausible. The event must be pharmacologically or phenomenologically definitive, with use of a satisfactory rechallenge procedure if necessary.
- Probably Related There is evidence to suggest a causal relationship, and the influence of other factors is unlikely. The clinical event, including an abnormal laboratory test result, occurs within a reasonable time after administration of the study intervention, is unlikely to be attributed to concurrent disease or other drugs or chemicals, and follows a clinically reasonable response on withdrawal (dechallenge). Rechallenge information is not required to fulfill this definition.
- Potentially Related There is some evidence to suggest a causal relationship (e.g., the event occurred within a reasonable time after administration of the trial medication). However, other factors may have contributed to the event (e.g., the participant's clinical condition, other concomitant events). Although an AE may rate only as "possibly related" soon after discovery, it can be flagged as requiring more information and later be upgraded to "probably related" or "definitely related", as appropriate.
- Unlikely to be related A clinical event, including an abnormal laboratory test result, whose temporal relationship to study intervention administration makes a causal relationship improbable (e.g., the event did not occur within a reasonable time after administration of the study intervention) and in which other drugs or chemicals or underlying disease provides plausible explanations (e.g., the participant's clinical condition, other concomitant treatments).
- Not Related The AE is completely independent of study intervention administration, and/or evidence exists that the event is definitely related to another etiology. There must be an alternative, definitive etiology documented by the clinician.

Expectedness

The Principal Investigator will be responsible for determining whether an AE is expected or unexpected. An AE will be considered unexpected if the nature, severity, or frequency of the event is not consistent with the risk information previously described for the study intervention.

Reporting

For studies conducted under an IND, there are two types of Safety Reports submitted to FDA:

- 7-Calendar-Day FDA Telephone or Fax Report: The sponsor-investigator will directly notify the FDA, within 7 calendar days after initial receipt of the information, of any adverse event that is fatal or life-threatening, unexpected, and considered at least possibly related to the investigational product.
- 15-Calendar-Day FDA Written Report: The sponsor-investigator will directly notify the FDA within 15 calendar days after initial receipt of the information, of any serious adverse event (other than those that are fatal or life-threatening) that is unexpected and considered at least possibly related to the investigational product.

Serious Adverse Events which do not meet the criteria for expedited reporting will be reported to the FDA in the IND Annual Report.

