6.4 Statistical Method

6.4.1 Statistical Design

6.4.2 Sample Size Considerations

Assume true probability of a participant survived and not needing any form of mechanical ventilation, high flow oxygen, or ECMO at day 14 is 40%. Randomizing 60 participants with a 1:1 ratio (tofacitinib+SOC: Placebo+SOC), the study will have 73% power (two-sided alpha=0.1) assuming an odds ratio of 3.5 for tofacitinib+SOC VS Placebo+SOC. No multiplicity adjustments will be performed for any secondary endpoint or exploratory endpoint analyses.

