7.11 Study Monitoring

7.12 Data Safety Monitoring Plan

A data safety monitoring board will be formed, comprised of clinicians at the site who are not named investigators in the study, to ensure intensive safety monitoring.

The DSMB will be responsible for monitoring the data, assuring protocol compliance, and conducting the safety reviews at the specified frequency. During the review process, the DSMB will evaluate whether the study should continue unchanged, require modification/amendment, or close to enrollment. Either the principal investigator, DSMB, or the IRB have the authority to stop or suspend the study or require modifications.

We do not view the risks associated with tofacitinib as minimal. Although we have assessed the proposed study as one of greater than minimal risk, the potential exists for anticipated and/or unanticipated adverse events, serious or otherwise, to occur since it is not possible to predict with certainty the absolute risk in any given individual or in advance of first-hand experience with the proposed study methods. Therefore, we will monitor the data and safety of the proposed study.

Attribution of Adverse Events:

Adverse events will be monitored for each subject participating in the study and attributed to the study procedures by the principal investigator [name] according to the following categories:

- a.) Definite: Adverse event is clearly related to investigational agent.
- b.) Probable: Adverse event is likely related to investigational agent.

- c.) Possible: Adverse event may be related to investigational agent.
- d.) Unlikely: Adverse event is likely not to be related to the investigational agent.
- e.) Unrelated: Adverse event is clearly not related to investigational agent.

Plan for Grading Adverse Events:

The following scale will be used in grading the severity of adverse events noted during the study:

- 1. Mild adverse event
- 2. Moderate adverse event
- 3. Severe

Serious Adverse Events:

In addition to grading the adverse event, the PI will determine whether the adverse event meets the criteria for a Serious Adverse Event (SAE). An adverse event is considered serious if it:

- 1. is life-threatening OR
- 2. results in in-patient hospitalization or prolongation of existing hospitalization OR
- 3. results in persistent or significant disability or incapacity OR
- 4. results in a congenital anomaly or birth defect OR
- 5. results in death OR

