**Figure 1. Study Schema**

### **3. ENDPOINTS AND BASELINE VARIABLES: DEFINITIONS AND CONVENTIONS**

#### **3.1. Primary Efficacy Endpoint(s)**

The primary objective is to determine whether tofacitinib improves the clinical outcomes of patients with moderate SARS-CoV-2 infection as determined by the primary outcome measure. The primary endpoint is proportion of subjects alive and not needing any form of mechanical ventilation, high flow oxygen, or ECMO by day 14.

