### 3.5. Safety Endpoints

#### 3.5.1. Adverse Events

An adverse event is considered a TEAE to a given treatment (for a participant who received at least of one dose of study intervention) if the event start date is on or after the treatment period start date and within 28 days of the treatment end date. The safety endpoints will be as follows.

- Incidence of TEAEs.
- Incidence of SAEs, and AEs leading to discontinuation.

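### COVID-19 progression can count as a serious adverse event and the SAP reports only pooled SAE incidence per arm, so a treatment benefit could mask serious drug harm; add a split beside the all-cause line

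*Protocol*

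**What the plan says.** Protocol 6.2.3 defines an AE without reference to cause: "Adverse event (AE) means any untoward medical occurrence associated with the use of an intervention in humans, whether or not considered intervention-related". An AE becomes serious by its outcome, in the view of the investigator or the sponsor. The outcomes include death, a life-threatening event, and "inpatient hospitalization or prolongation of existing hospitalization". Protocol 7.12 gives a second list, also without a causality condition, in which an event is serious if it "results in death OR" meets any other listed criterion. Neither section mentions progression of COVID-19 or events that are part of an efficacy endpoint.

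The same Protocol section requires a causality grade: "All AEs must have their relationship to study intervention assessed by the clinician who examines and evaluates the participant".

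The primary endpoint in SAP 3.1 is the proportion of subjects "alive and not needing any form of mechanical ventilation, high flow oxygen, or ECMO by day 14".

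For safety, SAP 3.5.1 plans the incidence of TEAEs and "Incidence of SAEs, and AEs leading to discontinuation". An event is treatment-emergent "if the event start date is on or after the treatment period start date and within 28 days of the treatment end date". SAP 6.5 sends these endpoints to the per-arm counts and exact confidence intervals of SAP 5.2.1. There is no split by progression or by causality, and no list of events of special interest. SAP 5.1 rules out hypothesis testing.

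**The concern.** A COVID-19 death by Day 14 is a primary failure and also an SAE, and so is an intubation judged life-threatening. The AEs leading to discontinuation share the problem: needing rescue therapy is a listed reason to stop study drug (Protocol 6.1.2 and 6.3.7), so worsening disease can enter that count too.

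Protocol 3.2.1 names serious infection, venous thromboembolism and gastrointestinal perforation as known risks of tofacitinib. If the drug prevents progression and also causes some of these events, the two effects push the pooled SAE percentage in opposite directions. The planned tables could then show similar or fewer SAEs on tofacitinib while drug-type serious harm is higher, and nothing in the planned AE tables would let a reader see it. The documents are also silent on whether progression is to be reported as an AE, so recording may vary between investigators.

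**Working it through.** **Inputs from the documents.** Protocol 6.4.2 gives 60 participants at 1:1, two-sided alpha 0.10, 40% success, and 73% power "assuming an odds ratio of 3.5 for tofacitinib+SOC VS Placebo+SOC". I read the 40% as the placebo rate. SAP 7 reports a safety review after 24 randomised subjects, with no further enrolment. The arm split of the 24 is not given; Protocol 5.1 says 1:1 and SAP 2.3 says 2:1.

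**Inputs I assume.** The documents give no SAE rate. Let *h* be the probability of a serious drug-type event: 3% on placebo and 10% on tofacitinib, independent of progression. Let *s* be the share of primary failures recorded as SAEs, varied from 1 to 0.1.

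**Step 1: the plan's own figure.** Odds on placebo are 0.4/0.6 = 0.667. Multiplied by 3.5 this is 2.333, so success on tofacitinib is 2.333/3.333 = 70%. With 30 per arm, a Wald test on the log odds ratio has 74.3% power, close to the stated 73%. Primary failure is therefore 60% versus 30%.

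**Step 2: expected pooled SAE incidence.** Per arm it is 1 − (1 − *s* × failure)(1 − *h*). For *s* = 1:

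- placebo: 1 − 0.40 × 0.97 = 61.2%
- tofacitinib: 1 − 0.70 × 0.90 = 37.0%

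The last column repeats the tofacitinib calculation with no effect on progression (60% failure in both arms).

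| Share *s* | Placebo | Tofacitinib, failure 30% | Tofacitinib, failure 60% |
|---|---|---|---|
| 1 | 61.2% | 37.0% | 64.0% |
| 0.5 | 32.1% | 23.5% | 37.0% |
| 0.25 | 17.6% | 16.8% | 23.5% |
| 0.1 | 8.8% | 12.7% | 15.4% |

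**Step 3: where the sign changes.** Set 0.97(1 − 0.6*s*) = 0.90(1 − 0.3*s*). Then 0.07 = (0.582 − 0.270)*s* = 0.312*s*, so *s* = 0.224. Above about 22% the expected pooled rate favours tofacitinib; below it the excess shows.

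**Step 4: other harm rates.** With 5% on placebo, the threshold is 17% for 10% harm on tofacitinib, 32% for 15% and 45% for 20%.

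**Step 5: what 24 participants would show.** This uses two independent binomials with harm of 3% versus 10% and the 60% versus 30% failure rates. With 12 per arm (an assumption), tofacitinib shows the lower observed SAE rate with probability 0.84, 0.60 and 0.41 for *s* = 1, 0.5 and 0.25. A 16:8 split gives 0.84, 0.60 and 0.43, so the unresolved allocation ratio hardly matters here. At *s* = 0.25 and 12 per arm the outcomes are 41% lower, 37% higher and 22% tied, which is close to a coin toss.

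**Step 6: no benefit on progression.** The true excess is 7 points. It shrinks to 64.0 − 61.2 = 2.8 points at *s* = 1 and 37.0 − 32.1 = 4.9 points at *s* = 0.5, but stays positive at every *s* in the table.

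**The case against.** A reader might infer that SAE incidence largely re-measures the primary endpoint. The documents do not support that. High flow oxygen and non-invasive ventilation are primary failures but not SAE criteria in themselves. The TEAE window runs to about Day 42 (14 + 28), well past Day 14. SAEs also cover infections, thrombosis and other events. No document gives the share of failures that would be recorded as SAEs.

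A reader might also infer that the pooled rate would make tofacitinib look safer in general. That needs a real benefit on progression of the size used for planning. Without it there is dilution only.

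The other side has further points. All-cause SAE incidence is standard and defensible, because an immunosuppressant could itself worsen viral pneumonia, and Protocol 6.2.3 says the study product must always be suspect. That stands, and it is why the all-cause line should remain the main one. The SAP is descriptive, with no safety decision rule. That is true, but readers will still set the two percentages side by side, and with few participants a handful of progression events can decide the direction. Mortality, ICU/ventilation status and laboratory abnormalities are tabulated separately, new infections are captured as AEs, and causality is graded. These show parts of the picture, but they do not take progression out of the SAE count, and the SAP does not tabulate causality.

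Finally, a split gains little precision at this size. With 12 per arm and true rates of 3% and 10%, the non-progression line shows a tofacitinib excess only 59% of the time. That limits what can be concluded from the split, but is no reason to omit it.

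**Conclusion.** The point holds in a limited form. The AE and SAE definitions take in COVID-19 progression, the SAP reports pooled incidence only, and the comparison can therefore overlap substantially with efficacy. Under the plan's own effect size and assumed harm of 3% versus 10%, the expected pooled SAE rate favours tofacitinib once more than about 22% of failures are recorded as SAEs. With 5% on placebo and 10% to 20% on tofacitinib, the threshold ranges from 17% to 45%.

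The result rests on the unstated overlap share, the assumed harm rates, independence of the two kinds of event, and a true benefit on progression. The actual extent of overlap cannot be established from the documents. This is a worthwhile, inexpensive addition to the safety tables; the planned all-cause analysis is not itself wrong.

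**What to change.** Amend SAP 3.5.1 and 6.5 as follows.

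- Keep all-cause SAEs, TEAEs and AEs leading to discontinuation as the main safety summary.
- Under each, add per arm: (i) events that are COVID-19 progression, by a definition fixed before database lock and applied blinded to treatment; (ii) all other events.
- Add a split by the causality grade already collected under Protocol 6.2.3.
- Show these lines beside all-cause death.
- State that the safety conclusion will not rest on line (ii) alone, since respiratory worsening may itself be drug-related.

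The cost is SAP wording, a few extra rows per table, and a short blinded classification of events from about 24 participants. Some events, such as respiratory failure with bacterial pneumonia, will need judgement; the retained all-cause line guards against misclassification. Intervals will be wide whichever line is read.
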